7.2.2 OTHER ASSAYS OR PROCEDURES

Exosome Purification: Mucus samples will be extracted from the PVA sponge by centrifugation (1500g at 4° C for 30 minutes). The mucus and irrigant samples will then be diluted in 150 µL of 1x phosphate buffered saline (PBS, Life Technologies, Carlsbad, CA) with Protease Inhibitor Cocktail (1:100, Sigma, St. Louis, MO). A portion of the whole mucus sample will be saved for cytokine analysis. Exosomes will then be isolated by ultracentrifugation (UCF) as described by Théry et al[63]. Cellular debris will be pelleted by centrifugation at 45 min at 12,000 × g at 4° C. The supernatant will then be suspended in 4.5mL of PBS in polypropylene tubes (Thinwall, 5.0 mL, 13 x 51 mm, Beckman Coulter, Indianapolis, IN) and ultracentrifuged for 2 hours at 110,000 × g, at 4° C. The supernatant will then be collected and the pellet will be resuspended in 4.5 mL 1x PBS. The suspension will be filtered through a

0.22- μ m filter (Fisher Scientific, Pittsburgh, PA) and collected in a fresh ultracentrifuge tube. The filtered suspension will then be centrifuged for 70 min at $110,000 \times g$ at 4°C. The supernatant will then be collected and the pellet will be resuspended in 200 μ l PBS with protease inhibitor. The exosome concentration of each pellet will be determined using a commercially available enzyme linked immunosorbent assay(ELISA) for the established exosome markers CD63 and CD9(ExoELISA, System Biosciences, Palo Alto, CA) as previously described[64].

Transmission Electron Microscopy(TEM): The presence of intact exosomes after UCF will be verified by TEM as previously described(Figure 3.5). Isolated exosomes will be fixed for 1 hour at room temperature in 2% paraformaldehyde in 0.1M sodium phosphate buffer (Electron Microscopy Sciences, Hatfield, PA). 5 μL of the exosomes will be absorbed on to Formvar-carbon coated electron microscopy grids (Electron Microscopy Sciences) for 20 minutes. After absorption, the grids will be rinsed in PBS 3 times and then transferred to PBS/50 mM glycine (Sigma Aldrich, St. Louis MO) for 4 washes. The grids will then be blocked in 5% Bovine Serum Albumin (BSA, Fisher Scientific) in 1x phosphate buffered saline (buffer) for 10 minutes at room temperature. The grids will then be incubated at 4°C overnight in the primary antibody (1:25, Purified Mouse Anti-Human CD63 Clone H5C6, BD Biosciences) diluted in 1% BSA buffer. The grids will then be rinsed in 0.1% BSA buffer and then 0.5% BSA buffer 6 times each. Then the secondary Protein-G antibody (1:20 in 1%BSA buffer, EM Grade, 10nm, Electron Microscopy Services, Hatfield, PA) in 5% BSA buffer will be applied for 1 hour at room temperature and rinsed 8 times with 1x PBS. The grids will be incubated in 1% glutaraldehyde in 0.1M sodium phosphate buffer (Electron Microscopy Services) for 5 minutes. After rinsing 8 times in deionized water, the grids will be contrasted in uranyl-oxalate solution, pH 7 (UA, Electron Microscopy Services) for 5 minutes. The grids will be blotted on filter paper and air dried prior to imaging. The exosomes will be observed using a FEI Tecnai G2 Spirit transmission electron microscope (FEI, Hillsboro, Oregon) at an accelerating voltage of 100 kV interfaced with an AMT XR41 digital CCD camera (Advanced Microscopy Techniques, Woburn, Massachusetts) for digital TIFF file image acquisition. Rabbit IgG (Vector Laboratories, Burlingame, CA) and CD63 lysate (Novus Biologicals CD63 Overexpression Lysate (Native), Fisher Scientific) will be used as negative and positive controls, respectively.

Exosomal P-gp, Whole Mucus, and Irrigant Th2 Cytokine Quantification: Whole mucus and exosomal P-gp will be quantified using a commercially available ELISA(USCN Life Sciences Inc., Wuhan, P.R. China) kit as previously described. Western blot will be used to confirm the ELISA findings. Briefly, 10 µg of total protein and Laemmli loading buffer (2x Laemmli sample buffer, Bio-Rad, Hercules, CA, with β-mercaptoethanol, Sigma, St. Louis, MO) will be denatured at 95°C for 3 minutes and separated on precast Novex® 4-20% Tris-Glycine Mini Protein Gels (1.0 mm, 9 wells, Life Technologies). Protein will be transferred onto a polyvinylidene fluoride membrane by iBlot® Dry Blotting System (Invitrogen, Carlsbad, CA). The membrane will be blocked and the primary antibody (Monoclonal Anti-P-glycoprotein Clone F4, 1:1000, in 5% milk in TBST) will be added and incubated at 4°C overnight. After 3 washes of 15 minutes each with TBST, the secondary antibody (Anti-Mouse IgG (Fab specific)-Peroxidase antibody produced in goat in 5% milk in TBST, Sigma) will be incubated for 1 hour at room temperature. The membrane will be washed again 3 times at 15 minutes each with TBST and SuperSignal™ West Pico Chemiluminescent Substrate (Life Technologies) will be applied for 5 minutes before visualization with ChemiDoc MP(Bio-Rad). Recombinant Pgp (USCN Life Sciences Inc., Wuhan, P.R. China) will be used as a control and a monoclonal anti-GAPDH antibody produced in mouse (Sigma Aldrich) will be used as a loading control. Pre and post-treatment Th2 associated cytokines in whole mucus and irrigant efflux including Eotaxin-3, Eosinophilic Cationic Protein(ECP), IL-6, IL-5, and TSLP which have been previously associated with successful CRSwNP treatment response[36][30][3][45] will be tested by commercially available ELISA.

7.2.3 SPECIMEN PREPARATION, HANDLING, AND STORAGE

Mucus will be taken from the middle meatus by placing a compressed polyvinyl alcohol sponge (PVA, Medtronic, Minneapolis, MN) within the internal valve for 5 minutes taking care not to abrade the mucosa or contaminate the sponge with blood. The irrigant efflux will be collected in sterile 50mL conical tubes. All samples will be stored in -80°C freezers in the Eaton-Peabody Laboratories(EPL) at MEEI.

7.2.4 SPECIMEN SHIPMENT

N/a

7.3 STUDY SCHEDULE

7.3.1 SCREENING

Phase 1B:

During the screening visit all exclusion/unclusion criteria will be reviewed. If a participant is a good candidate for the study consent will be obtained. Participants will be given an intake questionnaire which queires the presence of a variety of medical parameters which are relevant to the disease process. A pregnancy test will be administered to any female of child bearing age who is sexually active and not using contraception or admits to a possbility of being pregnant. If the participant has used systemic steroids within the past 3 weeks they will be asked to undergo a 3 week washout of steroids before beginning the trial.

Phase 2:

During the screening visit all exclusion/inclusion criteria will be reviewed. If a participant is a good candidate for the study consent will be obtained. Participants will be given an intake questionnaire which queires the presence of a variety of medical parameters which are relevant to the disease process. A pregnancy test will be administered to any female of child bearing age who is sexually active and not using contraception or admits to a pissbility of being pregnant. If the participant has used systemic steroids within the past 3 weeks they will be asked to undergo a 3 week washout of steroids before beginning the trial.

7.3.2 ENROLLMENT/BASELINE

Phase 1B:

Participants will fill out the baseline questionnaires (SNOT-22, VAS). An endoscopy will be recorded and scored. A mucus sample will be collected from the nasal cavity with a small sponge. Participants will be instructed in the proper method for using the verapamil irrigation. They will then be given a baseline EKG and asked to perform the first verapamil irrigation while being monitored for 1 hour by clinical monitoring equipment and study staff. After monitoring the patients will be given a second EKG. The irrigant will be collected. If no EKG abnormalities that are deemed unsafe by the study safety officer are detected during or after the initial irrigation the participants will be prescribed the rest of the verapamil rinse.

Phase 2:

Participants will fill out the baseline questionnaires (SNOT-22, VAS). An endoscopy will be recorded and scored. A mucus sample will be collected from the nasal cavity with a small sponge. Participants will be instructed in the proper method for using the verapamil irrigation. They will then be given a baseline EKG and asked to perform the

first verapamil irrigation while being monitored for 1 hour by clinical monitoring equipment and study staff. After monitoring the patients will be given a second EKG. The irrigant will be collected. If no EKG abnormalities that are deemed unsafe by the study safety officer are detected during or after the initial irrigation the participants will be prescribed the rest of the verapamil rinse.

7.3.3 FOLLOW-UP

Phase 1B:

Participants will asked to fill out a SNOT-22, VAS, , Satisfaction scale, and Compliance scale. Adherence to the treatment regimen will be evaluated. An endoscopy will be recorded and scored. A mucus sample will be collected from the nasal cavity with a small sponge. Participants will be evaluated for side-effects. An EKG will be taken. If no intermediate toxicity or DLT is experienced the participant will be moved up to the next dose. Participants will be asked to perform the initial irrigation of their next dose while being monitored for 1 hour by clinical monitoring equipment. After monitoring the patients will be given a second EKG. The irrigant will be collected. If no EKG abnormalities that are deemed unsafe by the study safety officer are detected during or after the initial irrigation the participants will be prescribed the rest of the verapamil rinse.

Phase 2:

During the Week 1 follow-up visit participants will asked to fill out a SNOT-22, VAS, , Satisscation scale, and Compliance scale. Adherence to the treatment regimen will be evaluated. Participants will be evaluated for side-effects. An EKG will be taken. An endoscopy will be recorded and scored.

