4 STUDY DESIGN AND ENDPOINTS

4.1 DESCRIPTION OF THE STUDY DESIGN

ARM 1: Phase 1B

The phase IB study will consist of an accelerated titration, intrapatient dose escalation cohort, with double-dose step design. The initial single patient cohort will begin by taking 0.3mg (10mg of Verapamil in 240mL of buffered normal saline yielding an established 3% residual nasal dose) as a nasal irrigation BID for 1 week. The first dose f

each escalation will be administered in a 10th or 11th floor MEE clinic withhemodynamic monitoring. A medically trained member of the study staff with monitor the patient for one hour. Patients will be instructed on the how to properly perform the irrigation using a pre-recorded video demonstration. If no first-course dose limiting toxicity (DLT, defined by the development of 2nd or 3rd degree heart block) is noted then patients will continue taking the current Verapamil rinse dose BID for 1 week. Dose escalation will occur weekly in the absence of a single, any course, DLT or a second, any course, intermediate toxicity(IT, defined by a heart rate of <50, an asymptomatic BP reduction >30% from baseline or systolic BP <90mmHg, an asymptomatic MAP reduction >30% from baseline or MAP<55, an asymptomatic diastolic BP reduction >30% from baseline, and a Meltzer Compliance Grade >4[60]). Each escalation will be a doubling of the dose from 0.3-2.4mg. At that point that dose will escalate in 0.6mg residual intervals for the rest of the trial up to a maximum of 3.6mg total residual dose. These doses were derived from the pharmacokinetic analysis of our oral Verapamil trial results. If a single, any course, DLT or second, any course, IT occurs, two additional patients will be recruited at that identified dose and Phase IB will revert to a standard 3+3 design. If any patient un-enrolls while the dose escalation is still occurring, they will be replaced to maintain 3 patient cohorts. The maximal administered dose(MAD) will be considered that at which at least 2 DLTs or 4 ITs occur and the MTD will then be assigned to the immediate preceeding dose.

At each weekly visit, the patients nasal endoscopy will be recorded for LKS grading, and they will be administered symptom, side-effect, and tolerability questionnaires. Pre-dosing mucus and post-dosing irrigant samples will also be atraumatically collected from the nasal cavity for use in exosomal biomarker sampling.

ARM 2: Phase 2

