6.1.7 STARTING DOSE AND DOSE ESCALATION SCHEDULE

Phase Ib Verapamil HCl dose will start at a total residual dose of 0.3mg. Dose escalations will be as follows: 0.3mg, 0.6mg, 1.2mg, 2.4mg, 3.0mg, 3.6mg. Participants will remain on a dose for at least one week before escalating.

Phase II dose will be determined by Phase Ib.

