6.1.8 DOSE ADJUSTMENTS/MODIFICATIONS/DELAYS

The Phase Ib dose will only be escalated if a participant has not experienced a DLT or 2 ITs on the previous dose. The Phase II dose will not be changed at any point during the 4 week course.

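### Section 7.3.3 moves a toxicity-free Phase Ib participant up without reference to the cohort, so during the 3+3 stage of Section 4.1 a participant may be taken above a dose still under evaluation

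*Combined protocol and SAP*

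**What the plan says.** Section 4.1 (Arm 1) starts with one patient: "The initial single patient cohort will begin by taking 0.3mg". The condition for going up is: "Dose escalation will occur weekly in the absence of a single, any course, DLT or a second, any course, intermediate toxicity". When it fails, "two additional patients will be recruited at that identified dose and Phase IB will revert to a standard 3+3 design". Stopping is counted by dose level: "The maximal administered dose(MAD) will be considered that at which at least 2 DLTs or 4 ITs occur". Once a dose has reached that count, Section 4.1 goes on to say that "the MTD will then be assigned to the immediate preceeding dose".

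Section 7.3.3 gives the instruction used at each weekly Phase Ib visit: "If no intermediate toxicity or DLT is experienced the participant will be moved up to the next dose".

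Section 6.1.8 is also worded by participant, but as a restriction: "The Phase Ib dose will only be escalated if a participant has not experienced a DLT or 2 ITs on the previous dose".

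Two other sections bear on when dosing ends. Section 10.4.7.1 halts the Phase Ib arm when the MTD has been determined. Section 7.3.4 lists reaching the maximal administered dose among the reasons for a final visit.

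**The concern.** The unit of the escalation decision differs between sections. From the trigger onward, Section 4.1 works by dose and cohort: patients are added at a dose, and events at that dose are counted. Section 7.3.3 works by individual: a clean week sends that person to the next dose. While the cohort is a single patient the two units coincide. They separate once Phase Ib changes to 3+3, and no section says which then governs.

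What is at stake is exposure. Staff following the visit instruction could give a participant a higher dose while the current one is unresolved because someone else has had a DLT there. The MTD is the Phase Ib primary endpoint, so the rule that leads to it should be readable in only one way.

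**Working it through.** The plan states no figure on this point, so there is none to reproduce. The check sets the rules side by side, traces one sequence through them, and then sizes it.

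**Rules by section**

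| Section | Unit | Effect |
|---|---|---|
| 4.1 | Phase and dose level | One DLT or a second IT stops escalation, adds two patients and starts 3+3; the MAD is at least 2 DLTs or 4 ITs at a dose |
| 7.3.3 | Individual | No IT and no DLT: the participant goes up |
| 6.1.8 | Individual | Necessary condition only; moves nobody up and does not carry over the cohort rule |
| 10.4.7.1 | Arm | Halts once the MTD is determined |
| 7.3.4 | Individual | Final visit on reaching the maximal administered dose |

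**Trace** (dose d is any level below the 3.6 mg top step)

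1. Patient A has a DLT at d. Under 4.1, escalation stops, B and C are added at d, and Phase Ib is now 3+3.
2. B completes a week with no IT or DLT. Under 7.3.3, B moves up. Dose d has one DLT, so the MAD has not been met, the MTD is not determined, and 10.4.7.1 does not apply.
3. C then has a DLT at d. Dose d now has two DLTs and is the MAD. B has already been dosed above it.

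**Size**

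Assumptions: each patient has the same DLT risk p at d, independently; B is assessed before C's event; B has no IT. The documents give no DLT rate, so p is shown over a range.

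- P(B is clean and moves up | A's DLT) = 1-p.
- P(B is clean, then C has a DLT | A's DLT) = (1-p) × p.

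| Assumed p | 1-p | p(1-p) |
|---|---|---|
| 0.05 | 0.95 | 0.05 × 0.95 = 0.048 |
| 0.10 | 0.90 | 0.10 × 0.90 = 0.09 |
| 0.20 | 0.80 | 0.20 × 0.80 = 0.16 |
| 0.33 | 0.67 | 0.33 × 0.67 = 0.22 |
| 0.50 | 0.50 | 0.50 × 0.50 = 0.25 |

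The chance that exactly one of B and C has a DLT is twice the last column, 2p(1-p). The other half is the reverse order: the DLT comes first, the MAD is met, and the arm is halted before the clean participant's visit. Only the order traced above counts, hence p(1-p).

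**Other safeguards.** The safety officer's check in 7.3.3 concerns EKG abnormalities around the monitored irrigation, not cohort status. DSMB review in Section 9 follows enrolment counts (after the first 3 participants, then every 6), not dose levels. Neither is written to catch step 2.

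**The case against.** The strongest reply is that Section 4.1 is the design section and 7.3.3 only lists visit procedures. A sensible team would let 4.1 govern, and 6.1.8 is compatible with a cohort rule. Also, 4.1 qualifies toxicity by course and does not speak of any participant's toxicity, so the phase-level reading is an inference. Both remarks are fair. The inference is nevertheless sound, because 4.1 changes the whole phase to 3+3 and counts the MAD by dose. And 7.3.3 is an affirmative instruction with no exception for the 3+3 stage. Nothing ranks one section above the other.

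Several stronger readings are tempting and are not supported:

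- **That a participant can be moved above a dose that has already met the MAD.** Once the MAD is met, 4.1 assigns the MTD and 10.4.7.1 halts the arm. Section 7.3.4 points the same way, although it may mean the top dose. The gap lies between the 4.1 trigger and the MAD.
- **That 6.1.8 itself escalates participants.** It only restricts escalation.
- **That 6.1.7 contradicts 4.1 on where added patients enter.** "Phase Ib Verapamil HCl dose will start at a total residual dose of 0.3mg" gives the first step of the schedule; 4.1 separately places the added patients at the identified dose.
- **That the two rules yield different MTDs.** Only 4.1 defines the MAD and MTD. In the trace, d remains the MAD whether or not B moves up.
- **That carrying tolerant participants upward biases the MTD by a calculable amount.** Intrapatient escalation is a stated design choice, and any figure would need assumed risks at two doses and perfectly stable individual tolerance.

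**Conclusion.** The point holds as a conflict between stated rules with a safety consequence. Followed literally, 7.3.3 can take a toxicity-free participant above a dose that 4.1 has put under 3+3 evaluation, and the halting rule in 10.4.7.1 comes too late to prevent that move. Given a triggering DLT, the chance that the dose then proves to be the MAD by the traced route is 9%, 16% and 22% at assumed DLT risks of 0.10, 0.20 and 0.33. It cannot exceed 25% at any p.

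These figures depend on the assumed p, on independence, and on B being assessed before C's event. They leave out ITs, which could hold B back or add to the MAD count. They illustrate the size of the gap and are not estimates for this drug. The textual conflict does not depend on them.

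**What to change.** Reconcile Sections 4.1, 6.1.8, 7.3.3, 7.3.4 and 10.4.7.1 so that one stated rule says:

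- whether escalation in the 3+3 stage is decided by participant or by cohort;
- what happens to toxicity-free participants while a dose is under evaluation.

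Sections 6.1.8 and 7.3.3 should then refer to that rule and not carry versions of their own. The same edit should settle the IT count: 7.3.3 moves a participant up on no IT at all, 6.1.8 refers to two on the previous dose, and 4.1 to a second in any course.

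Which rule to adopt is for the investigators, the sponsor and the DSMB; no dose or clinical rule is proposed here. The cost is wording in a handful of sections. Depending on how they are reconciled, participants may have to wait for a cohort decision before moving.

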7.3.4 FINAL STUDY VISIT

Phase 1B:

Participants will have their final study visit when they experience DLT and are removed from the study, choose to end their participation, or achive the maximal administered dose. The reason for the drop-out will be noted in the participant file. Participants will be asked to fil out a SNOT-22, VAS, Satisfaction scale, and Compliance scale and will be evaluated for side-effects. An endoscopy will be recorded and scored. A mucus sample will be collected from the nasal cavity with a small sponge. Participants will receive their compensation at the end of the final visit.

Phase 2:

During the Week 4 visit participants will be asked to fill out a SNOT-22, VAS, Satisfaction scale, and Compliance scale. Adherence to the treatment regimen will be evaluated. Participants will be evaluated for side-effects. An endoscopy will be recorded and scored. A mucus sample will be collected from the nasal cavity with a small sponge. Participants will receive their compensation at the end of the final visit.

7.3.5 EARLY TERMINATION VISIT

In the event of an early termination participants will be asked to perform all the procedures for the final visit (Phase 1B and 2) at their final visit.

7.3.7 SCHEDULE OF EVENTS TABLE

4	Phase Ib			Phase II			
Procedures	Screening	Enrollment/ Baseline	Weekly/Final Follow-up	Screening	Enrollment/ Baseline	Follow-up (Day 7)	Final Visit (Day 28)
Informed Consent (IC)	X		-	х			
Intake Form (IF)	X	3	į	x		3	
Pregnancy Test (PT)	X			x			
SNOT-22	100	х	х		х	х	X
Visual Analog Scale (VAS)	3	х	x		х	х	X
Electrocardiogram (EKG)		х	х		x	x	
Heart Rate (HR)		х	х		х	х	X
Blood Pressure (BP)	ŝ.	x	x		x	x	х
Lund-Kennedy Score (LKS)		x	x		х	x	X
Nasal irrigation (NI)		х	х		х		х
Mucus sponge (MS)	ý.	x	х		x	- 3	х
Satisfaction Scale (SS)		d	x			Х	х
Compliance Scale (CS)			×			×	х
Side effects (SE)			x			х	X

7.4 JUSTIFICATION FOR SENSITIVE PROCEDURES

N/a

7.5 CONCOMITANT MEDICATIONS, TREATMENTS, AND PROCEDURES

7.5.1 PRECAUTIONARY MEDICATIONS, TREATMENTS, AND PROCEDURES

Participants will be asked to abstain from consuming grapefruit, limes, or pomelos while using the study medication.

7.6 PROHIBITED MEDICATIONS, TREATMENTS, AND PROCEDURES

The following drugs will not be permitted for concomitant use with Verapamil HCI: AspirinBeta-blockers, Cimetidine(Tagamet), Clarithromycin(Biaxin), Cyclosporin, Digoxin, Disopyramide(Norpace), Diuretics, Erythromycin, Flecainide, HIV Protease Inhibitors(Indinavir, Nelfinavir, Ritonavir), Quinidine, Lithium, Pioglitazone, Rifampin, and St Johns Wort.

7.7 PROPHYLACTIC MEDICATIONS, TREATMENTS, AND PROCEDURES

N/a

7.8 RESCUE MEDICATIONS, TREATMENTS, AND PROCEDURES

N/a

7.9 PARTICIPANT ACCESS TO STUDY AGENT AT STUDY CLOSURE

Participants will not have access to intranasal Verapamil HCl after the trial.

8 ASSESSMENT OF SAFETY

8.1 SPECIFICATION OF SAFETY PARAMETERS

Safety parameters that are also endpoints for Phase Ib are:

- a development of 2nd or 3rd degree heart block as measured by an EKG.
- a heart rate of <50
- an asymptomatic BP reduction >30% from baseline or SBP <90mmHg
- an asymptomatic AMP reduction >30% from baseline or MAP<55
- an asymptomatic DBP reduction >30% from baseline

All safety parameters will be recorded in a partcipants CRF at each study visit. All AEs will require reporting for the protection of human subjects.

If a heart block develops, treatment will be adjusted based on symptomatology. Completely asymptomatic patients can be observed. Patients with mild to moderate symptoms (hypotension, orthostasis, fatigue, dyspnea or angina) should be treated with 1liter NS bolus followed by Calcium Gluconate. Patients who are severely symptomatic and have failed the above interventions can also receive glucagon, norepinephrine, and finally pacing if necessary

